8.4.2.2 Infusion-related Reactions

Grade 1	
 • The infusion rate of MEDI4736 may be decreased 50% or temporarily interrupted until resolution of the event. • Acetaminophen and/or antihistamines may be administered per institutional standards at the discretion of the Investigator. • Premedication for subsequent doses should be considered. • Steroids should not be used for routine premedication of \leqGrade 2 infusion reactions
Grade 2	
 • Same as Grade 1, but consider giving subsequent infusions at 50% of the initial infusion rate.
Grade 3-4	
 • The infusion must be stopped immediately and treatment permanently discontinued. • Manage severe infusion-related reactions per institutional standards (e.g., IM epinephrine, followed by IV diphenhydramine and ranitidine, and IV glucocorticoid).

CONFIDENTIAL

8.4.2.3 All other Adverse Events

Grade 1	
No dose modification required.
Grade 2	
Hold MEDI4736 until resolution to \leq Grade 1 or baseline, and discontinue MEDI4736 permanently if such resolution does not occur within 60 days.
Grade 3	
Hold MEDI4736. If AEs downgrade to \leq Grade 2 within 7 days or resolve to \leq Grade 1 or baseline within 14 days, resume MEDI4736 administration at next scheduled dose. Otherwise, discontinue MEDI4736 permanently.
Grade 4	
In general, discontinue MEDI4736 permanently.For isolated lab results, decision to discontinue should be based on accompanying clinical signs/symptoms and per Investigator's clinical judgment and in consultation with the Sponsor.

8.4.3 MEDI4736 Dose Modifications Not Due to Toxicities

MEDI4736 administration may be modified or discontinued as a result of events other than toxicity, e.g., intercurrent illness or logistical/administrative reasons, whereby the following rules should apply (after consultation with the Medical Monitor, if necessary):

1. The originally planned visit/treatment schedule should be maintained in general, i.e., dosing interruptions should not reset the original treatment schedule. Exceptions may be made only for individual dosing days, whereby the interval between any two doses shall be no less than 21 days (for subjects on Q2W dosing, the interval shall be no less than 10 days). All resulting protocol deviations should be documented.
2. If the dosing interruption causes 2 consecutive planned doses to be missed, the treatment should be discontinued.
3. If the dosing interruption is \leq half the planned dosing interval, the originally planned dose should be given and the next dose(s) should be adjusted in accordance with #1, if necessary.
4. If the dosing interruption is greater than half the planned dosing interval, the dose should be skipped and the next dose(s) should be adjusted in accordance with #1, if necessary.

C O N F I D E N T I A L

8.5 RECIST 1.1 Guidelines

This section outlines the revised Response Evaluation Criteria in Solid Tumors (RECIST) guideline (version 1.1) as published (53) and as summarized by NCI for CTEP-involved clinical trials. Changes in the largest diameter (unidimensional measurement) of the tumor lesions and the shortest diameter in the case of malignant lymph nodes are used in the RECIST criteria.

8.5.1 Disease Parameters

Measurable disease. Measurable lesions are defined as those that can be accurately measured in at least one dimension (longest diameter to be recorded) as ≥ 20 mm by chest x-ray, as ≥ 10 mm with CT scan, or ≥ 10 mm with calipers by clinical exam. All tumor measurements must be recorded in millimeters (or decimal fractions of centimeters).

Note: Tumor lesions that are situated in a previously irradiated area might or might not be considered measurable. *If the investigator thinks it appropriate to include them, the conditions under which such lesions should be considered must be defined in the protocol.*

Malignant lymph nodes. To be considered pathologically enlarged and measurable, a lymph node must be ≥ 15 mm in short axis when assessed by CT scan (CT scan slice thickness recommended to be no greater than 5 mm). At baseline and in follow-up, only the short axis will be measured and followed.

Non-measurable disease. All other lesions (or sites of disease), including small lesions (longest diameter < 10 mm or pathological lymph nodes with ≥ 10 to < 15 mm short axis), are considered non-measurable disease. Bone lesions, leptomeningeal disease, ascites, pleural/pericardial effusions, lymphangitis cutis/pulmonitis, inflammatory breast disease, and abdominal masses (not followed by CT or MRI), are considered as non-measurable.

Note: Cystic lesions that meet the criteria for radiographically defined simple cysts should not be considered as malignant lesions (neither measurable nor non-measurable) since they are, by definition, simple cysts.

'Cystic lesions' thought to represent cystic metastases can be considered as measurable lesions, if they meet the definition of measurability described above. However, if non-cystic lesions are present in the same subject, these are preferred for selection as target lesions.

Target lesions. All measurable lesions up to a maximum of 2 lesions per organ and 5 lesions in total, representative of all involved organs, should be identified as **target lesions** and recorded and measured at baseline. Target lesions should be selected on the basis of their size (lesions with the longest diameter), be representative of all involved organs, but in addition should be those that lend themselves to reproducible repeated measurements. It may be the case that, on occasion, the largest lesion does not lend itself to reproducible measurement in which circumstance the next largest lesion which can be measured reproducibly should be selected. A sum of the diameters (longest for non-nodal lesions, short axis for nodal lesions) for all target lesions will be calculated and reported as the baseline sum diameters. If lymph nodes are to be included in the sum, then only the short axis is added into the sum. The baseline sum diameters will be used as reference to further characterize any objective tumor regression in the measurable dimension of the disease.

CONFIDENTIAL

Non-target lesions. All other lesions (or sites of disease) including any measurable lesions over and above the 5 target lesions should be identified as **non-target lesions** and should also be recorded at baseline. Measurements of these lesions are not required, but the presence, absence, or in rare cases unequivocal progression of each should be noted throughout follow-up.

8.5.2 Methods for Evaluation of Measurable Disease

All measurements should be taken and recorded in metric notation using a ruler or calipers. All baseline evaluations should be performed as closely as possible to the beginning of treatment and never more than 4 weeks before the beginning of the treatment.

The same method of assessment and the same technique should be used to characterize each identified and reported lesion at baseline and during follow-up. Imaging-based evaluation is preferred to evaluation by clinical examination unless the lesion(s) being followed cannot be imaged but are assessable by clinical exam.

Clinical lesions: Clinical lesions will only be considered measurable when they are superficial (e.g., skin nodules and palpable lymph nodes) and ≥ 10 mm diameter as assessed using calipers (e.g., skin nodules). In the case of skin lesions, documentation by color photography, including a ruler to estimate the size of the lesion, is recommended.

Chest x-ray: Lesions on chest x-ray are acceptable as measurable lesions when they are clearly defined and surrounded by aerated lung. However, CT is preferable.

Conventional CT and MRI: This guideline has defined measurability of lesions on CT scan based on the assumption that CT slice thickness is 5 mm or less. If CT scans have slice thickness greater than 5 mm, the minimum size for a measurable lesion should be twice the slice thickness. MRI is also acceptable in certain situations (e.g. for body scans).

Use of MRI remains a complex issue. MRI has excellent contrast, spatial, and temporal resolution; however, there are many image acquisition variables involved in MRI, which greatly impact image quality, lesion conspicuity, and measurement. Furthermore, the availability of MRI is variable globally. As with CT, if an MRI is performed, the technical specifications of the scanning sequences used should be optimized for the evaluation of the type and site of disease. Furthermore, as with CT, the modality used at follow-up should be the same as was used at baseline and the lesions should be measured/assessed on the same pulse sequence. It is beyond the scope of the RECIST guidelines to prescribe specific MRI pulse sequence parameters for all scanners, body parts, and diseases. Ideally, the same type of scanner should be used and the image acquisition protocol should be followed as closely as possible to prior scans. Body scans should be performed with breath-hold scanning techniques, if possible.

PET-CT: At present, the low dose or attenuation correction CT portion of a combined PET-CT is not always of optimal diagnostic CT quality for use with RECIST measurements. However, if the site can document that the CT performed as part of a PET-CT is of identical diagnostic quality to a diagnostic CT (with IV and oral contrast), then the CT portion of the PET-CT can be used for RECIST measurements and can be used interchangeably with conventional CT in accurately measuring cancer lesions over time. Note, however, that the PET portion of the CT introduces additional data which may bias an investigator if it is not routinely or serially performed.

CONFIDENTIAL

Ultrasound: Ultrasound is not useful in assessment of lesion size and should not be used as a method of measurement. Ultrasound examinations cannot be reproduced in their entirety for independent review at a later date and, because they are operator dependent, it cannot be guaranteed that the same technique and measurements will be taken from one assessment to the next. If new lesions are identified by ultrasound in the course of the study, confirmation by CT or MRI is advised. If there is concern about radiation exposure at CT, MRI may be used instead of CT in selected instances.

Endoscopy, Laparoscopy: The utilization of these techniques for objective tumor evaluation is not advised. However, such techniques may be useful to confirm complete pathological response when biopsies are obtained or to determine relapse in trials where recurrence following complete response (CR) or surgical resection is an endpoint.

Tumor markers: Tumor markers alone cannot be used to assess response. If markers are initially above the upper normal limit, they must normalize for a subject to be considered in complete clinical response. Specific guidelines for both CA-125 response (in recurrent ovarian cancer) and PSA response (in recurrent prostate cancer) have been published.(54-56) In addition, the Gynecologic Cancer Intergroup has developed CA-125 progression criteria which are to be integrated with objective tumor assessment for use in first-line trials in ovarian cancer.(57)

Cytology, Histology: These techniques can be used to differentiate between partial responses (PR) and complete responses (CR) in rare cases (e.g., residual lesions in tumor types, such as germ cell tumors, where known residual benign tumors can remain).

The cytological confirmation of the neoplastic origin of any effusion that appears or worsens during treatment when the measurable tumor has met criteria for response or stable disease is mandatory to differentiate between response or stable disease (an effusion may be a side effect of the treatment) and progressive disease.

FDG-PET: While FDG-PET response assessments need additional study, it is sometimes reasonable to incorporate the use of FDG-PET scanning to complement CT scanning in assessment of progression (particularly possible 'new' disease). New lesions on the basis of FDG-PET imaging can be identified according to the following algorithm:

- a) Negative FDG-PET at baseline, with a positive FDG-PET at follow-up is a sign of PD based on a new lesion.
- b) No FDG-PET at baseline and a positive FDG-PET at follow-up: If the positive FDG-PET at follow-up corresponds to a new site of disease confirmed by CT, this is PD. If the positive FDG-PET at follow-up is not confirmed as a new site of disease on CT, additional follow-up CT scans are needed to determine if there is truly progression occurring at that site (if so, the date of PD will be the date of the initial abnormal FDG-PET scan). If the positive FDG-PET at follow-up corresponds to a pre-existing site of disease on CT that is not progressing on the basis of the anatomic images, this is not PD.
- c) FDG-PET may be used to upgrade a response to a CR in a manner similar to a biopsy in cases where a residual radiographic abnormality is thought to represent fibrosis or scarring. The use of FDG-PET in this circumstance should be prospectively described in the protocol and supported by disease-specific medical literature for the indication.

CONFIDENTIAL

However, it must be acknowledged that both approaches may lead to false positive CR due to limitations of FDG-PET and biopsy resolution/sensitivity.

Note: A 'positive' FDG-PET scan lesion means one which is FDG avid with an uptake greater than twice that of the surrounding tissue on the attenuation corrected image.

8.5.3 Response Criteria

8.5.3.1 Evaluation of Target Lesions

Complete Response (CR): Disappearance of all target lesions. Any pathological lymph nodes (whether target or non-target) must have reduction in short axis to <10 mm.

Partial Response (PR): At least a 30% decrease in the sum of the diameters of target lesions, taking as reference the baseline sum diameters

Progressive Disease (PD): At least a 20% increase in the sum of the diameters of target lesions, taking as reference the smallest sum on study (this includes the baseline sum if that is the smallest on study). In addition to the relative increase of 20%, the sum must also demonstrate an absolute increase of at least 5 mm. (Note: the appearance of one or more new lesions is also considered progressions).

Stable Disease (SD): Neither sufficient shrinkage to qualify for PR nor sufficient increase to qualify for PD, taking as reference the smallest sum diameters while on study

8.5.3.2 Evaluation of Non-Target Lesions

Complete Response (CR): Disappearance of all non-target lesions and normalization of tumor marker level. All lymph nodes must be non-pathological in size (<10 mm short axis)

Note: If tumor markers are initially above the upper normal limit, they must normalize for a subject to be considered in complete clinical response.

Non-CR/Non-PD: Persistence of one or more non-target lesion(s) and/or maintenance of tumor marker level above the normal limits

Progressive Disease (PD): Appearance of one or more new lesions and/or *unequivocal progression* of existing non-target lesions. *Unequivocal progression* should not normally trump target lesion status. It must be representative of overall disease status change, not a single lesion increase.

Although a clear progression of "non-target" lesions only is exceptional, the opinion of the treating physician should prevail in such circumstances, and the progression status should be confirmed at a later time by the review panel (or Principal Investigator).

8.5.3.3 Evaluation of Best Overall Response

The best overall response is the best response recorded from the start of the treatment until disease progression/recurrence (taking as reference for progressive disease the smallest measurements recorded since the treatment started). The subject's best response assignment will depend on the achievement of both measurement and confirmation criteria.

C O N F I D E N T I A L

For Subjects with Measurable Disease (i.e., Target Disease)

Target Lesions	Non-Target Lesions	New Lesions	Overall Response	Best Overall Response when Confirmation is Required*
CR	CR	No	CR	≥4 wks. Confirmation**
CR	Non-CR/Non-PD	No	PR	≥4 wks. Confirmation**
CR	Not evaluated	No	PR	
PR	Non-CR/Non-PD/not evaluated	No	PR	
SD	Non-CR/Non-PD/not evaluated	No	SD	documented at least once ≥4 wks. from baseline**
PD	Any	Yes or No	PD	no prior SD, PR or CR
Any	PD***	Yes or No	PD	
Any	Any	Yes	PD	

* See RECIST 1.1 manuscript for further details on what is evidence of a new lesion.
 ** Only for non-randomized trials with response as primary endpoint.
 *** In exceptional circumstances, unequivocal progression in non-target lesions may be accepted as disease progression.
 Note: Subjects with a global deterioration of health status requiring discontinuation of treatment without objective evidence of disease progression at that time should be reported as “*symptomatic deterioration.*” Every effort should be made to document the objective progression even after discontinuation of treatment.

For Subjects with Non-Measurable Disease (i.e., Non-Target Disease)

Non-Target Lesions	New Lesions	Overall Response
CR	No	CR
Non-CR/non-PD	No	Non-CR/non-PD*
Not all evaluated	No	not evaluated
Unequivocal PD	Yes or No	PD
Any	Yes	PD

* ‘Non-CR/non-PD’ is preferred over ‘stable disease’ for non-target disease since SD is increasingly used as an end-point for assessment of efficacy in some trials so to assign this category when no lesions can be measured is not advised.

8.5.3.4 Duration of Response

Duration of overall response: The duration of overall response is measured from the time measurement criteria are met for CR or PR (whichever is first recorded) until the first date that recurrent or progressive disease is objectively documented (taking as reference for progressive disease the smallest measurements recorded since the treatment started).

The duration of overall CR is measured from the time measurement criteria are first met for CR until the first date that progressive disease is objectively documented.

Duration of stable disease: Stable disease is measured from the start of the treatment until the criteria for progression are met, taking as reference the smallest measurements recorded since the treatment started, including the baseline measurements.

8.6 irRECIST Guidelines

Determination of response via irRECIST should take into consideration all target and non-target lesions.

A key distinction between standard RECIST 1.1 criteria and immune-related response criteria is that irRECIST requires early evidence of progressive disease (i.e., a determination of irPD \leq 12 weeks after starting study treatment) be confirmed by repeat, consecutive imaging \geq 4 weeks after the initial documentation in the absence of rapid clinical deterioration. During this interim \geq 4 week period, subjects should continue to be followed per protocol, including continued dosing of the study drug(s).

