3.1.10 Subject Withdrawal from Treatment or Study

A subject will be **withdrawn from study treatment** for any of the following reasons:

1. Withdrawal of consent for further treatment.
2. Pregnancy or intent to become pregnant.
3. Dose-limiting toxicity at any time (see Section 3.1.9 for definition of DLT and permitted continuation).
4. Confirmation of progressive disease by irRECIST criteria requiring alternative treatment.
5. Significant protocol violation or noncompliance that, in the opinion of the Investigator or Sponsor, warrants withdrawal.
6. Development of intercurrent, non-cancer related illnesses or complications that prevent either continuation of therapy or regular follow-up.
7. Best medical interest of the subject (at the discretion of the Investigator)

Discontinuation from receiving study treatment does not mean that the subject is withdrawn from the study. If feasible, subjects who are withdrawn from study treatment should enter the On Study Follow-Up, followed by the Post Study Follow-up (see Sections 3.1.16 and 3.2).

Subjects who begin other anti-cancer therapy should immediately be considered off-study and proceed to the Post Study Follow-up (see Section 3.1.16).

A subject will be **withdrawn from the study** for the following reasons:

1. Best medical interest of the subject at the discretion of the Investigator.
2. Initiation of alternative anti-cancer therapy including marketed or another investigational agent.
3. Withdrawal of consent for all follow-up.
4. Lost to follow-up.
5. Death

General subject withdrawal criteria are outlined in the Administrative, Legal and Ethical Requirements section of the protocol (see Section 7.2.6).

See also Sections 8.2, 8.3, and 8.4 for subject withdrawal from treatment due to necessary dosing interruptions or discontinuations.

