3.1.10.1 Treatment beyond Progression

Subjects meeting criteria for progression by RECIST 1.1 will be allowed to continue on therapy until confirmation of progression if the subject agrees and signs an appropriate informed consent form regarding continuation of treatment and as long as the following criteria are met at the discretion of the Investigator:

- a. Absence of symptoms and signs (including worsening of laboratory values) indicating disease progression;
- b. No significant decline in ECOG performance status;
- c. Absence of rapid progression of disease or of progressive tumor at critical anatomical sites (e.g., cord compression) requiring urgent alternative medical intervention.

See Section 8.5 for additional information regarding RECIST 1.1.

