c - An aliquot of the PBMC and/or Tumor Biopsy/Archival Tissue will be used for pharmacogenomics - a separate sampling is not needed																						
d - See section 7.1.5 for details regarding collection of AEs for 90 days after last study drug administration.																						
e - Biopsy is optional for Phase 1. Refer to Criterion 4 in Section 5.1. Archival tissue will be requested for all subjects, preferably from primary tumor site prior to cancer treatment; however, archival tissue is not a requirement for study entry.																						
f - Pregnancy tests are not required for subjects who are not of child-bearing potential as defined in Section 5.2, # 17																						
g - Screening/Baseline specimens for correlative assessments may be collected up to Cycle 1/Day 1 prior to the PLD dose.																						
h - See Section 3.1.16 regarding assessments scheduled for both the last on treatment visit and the first post-last treatment visit.																						
i - Standard of Care procedures may be used for eligibility assessments provided they meet the criteria specified in either the inclusion criteria or flowchart																						

Every 3 months for 3 years from initiation of treatment. Clinical outcomes data (dates of progression/relapse and survival) will be recorded (See Section 3.1.16).

CONFIDENTIAL

Study Flowchart for All Subjects Except Dose Level 0a Cohort	Screening/ Baseline	Treatment											
		Cycle 1		Cycle 2		Cycle 3		Cycle 4		Cycle 5		Cycle 6	
Cycle week		1		1		1		1		1		1	
Visit Day per Cycle	-28 to -1	1	3±1	1±3	3±1	1±3	3±1	1±3	3±1	1±3	3±1	1±3	3±1
Target Cumulative Visit Day		1	3	29	31	57	59	85	87	113	115	141	143
Phase 1 & 2 STUDY DRUG ADMINISTRATION													
Pegylated liposomal doxorubicin - PLD (IV)		X		X		X		X		X		X	
MEDI4736 (IV)			X		X		X		X		X		X
Tumor & Disease Assessments													
Disease Staging (date/stage at 1st diagnosis and at study entry)	X												
Disease Assessment by RECIST 1.1 and irRECIST (including appropriate imaging)	-14 to -1							X					
Study Procedures & Examinations													
Eligibility Assessment and Informed Consent (IC) ⁱ	X												
Demographics (incl. DoB; sex; race; ethnicity)	X												
Medical history	X												
Physical Exam (incl. weight and ECOG Perf Status)	X	X		X		X		X		X		X	
Height	X												
Vital Signs (T, HR, BP, RR) ^b	X	X	X	X	X	X	X	X	X	X	X	X	X
12-Lead ECG ^a	X			X		X		X		X		X	
Echocardiogram or MUGA	X								X				X

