i - Standard of Care procedures may be used for eligibility assessments provided they meet the criteria specified in either the inclusion criteria or flowchart													

CONFIDENTIAL

Study Flowchart for All Subjects Except Dose Level 0a Cohort (Cont)	Treatment												On Study Follow-up			Post Study Follow-Up
	Cycle 7		Cycle 8		Cycle 9		Cycle 10		Cycle 11		Cycle 12		Last Study Drug Administration	Last Study Drug Administration	Last Study Drug Administration	
Cycle week	1		1		1		1		1		1		+28 ±3 days ^h	+56 ±7 days	+90 ±7 days End of Study	
Visit Day per Cycle	1±3	3±1	1±3	3±1	1±3	3±1	1±3	3±1	1±3	3±1	1±3	3±1				
Target Cumulative Visit Day	169	171	197	199	225	227	253	255	281	283	309	311				
Phase 1 & 2 STUDY DRUG ADMINISTRATION																
Pegylated liposomal doxorubicin - PLD (IV)	X		X		X		X		X		X					
MEDI4736 (IV)		X		X		X		X		X		X				
Tumor & Disease Assessments																
Disease Staging (date/stage at 1st diagnosis and at study entry)																
Disease Assessment by RECIST and irRECIST (including appropriate imaging)	X							X					+84 ± 7 days from last disease assessment			
Study Procedures & Examinations																
Eligibility Assessment and Informed Consent (IC) ⁱ																
Demographics (incl. DoB; sex; race; ethnicity)																
Medical history																
Physical Exam (incl. weight and ECOG Perf Status)	X		X		X		X		X		X		X	X	X	
Height																
Vital Signs (T, HR, BP, RR) ^b	X	X	X	X	X	X	X	X	X	X	X	X	X	X	X	
12-Lead ECG ^a	X		X		X		X		X		X		X		X	
Echocardiogram or MUGA						X							X			
Concomitant Medication / Procedure (name, indication, dose, route, start & end dates)	X	X	X	X	X	X	X	X	X	X	X	X	X	X	X	
Adverse Events (starting or worsening after IC) ^d	X	X	X	X	X	X	X	X	X	X	X	X	X	X	X	
Specimens for Laboratory Procedures																
Blood Hematology (complete blood count, differential, platelets) ^a	X	X	X	X	X	X	X	X	X	X	X	X	X	X	X	
Chemistry (gluc., BUN, crea., Na, K, Ca, Cl, CO2, PO4, Mg, prot., alb., Tbili., AST, ALT, ALP, LDH) ^a	X	X	X	X	X	X	X	X	X	X	X	X	X	X	X	
Chemistry cont. (Amylase and lipase) ^a	X	X	X	X	X	X	X	X	X	X	X	X	X	X	X	
Chemistry cont. (Free T3, Free T4, TSH) ^a	X		X		X		X		X		X		X	X	X	
Serum pregnancy test ^{a,f}	X				X				X				X		X	
CA-125 ^a	X		X		X		X		X		X		X			
Urine Pregnancy Test ^{a,f}																
Specimens for Correlative Assessments																
PBMC/Plasma Collection & Banking ^{a,g}	X												X		X	
MDSC (Seramatrix) ^{a,g} (US sites only)	X												X			

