PFS time will be summarized for each cohort and phase and will include the 25th percentile, median, 75th percentile, corresponding 95% CIs, minimum and maximum, where PFS time will be calculated using the Kaplan-Meier method. In addition, PFS will be presented graphically.

PFS time is defined as time from the start date of the treatment (Day 1) to the first occurrence of confirmed progression (clinical or radiological), or the date of death due to any cause, whichever occurs first. Subjects without documentation of progression at the time of the analysis will be censored at the date of the last tumor response assessment, date of start of alternate therapy, or last contact if in post study follow-up, whichever comes first. Subjects with no tumor response assessment will be censored at the start date of the treatment.

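### No rule says how an early irPD that is never re-imaged is counted; under SAP 3.8.1 it can be censored near Day 85, which biases the secondary irRECIST PFS results upward

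*Protocol*

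**What the plan says.** **Confirmation rule.** Protocol 8.6 (opening text of the irRECIST guidelines) says that irPD determined 12 weeks or less after the start of treatment must "be confirmed by repeat, consecutive imaging" at least 4 weeks after it was first documented, "in the absence of rapid clinical deterioration". Follow-up and dosing continue meanwhile. There is a minimum interval but no maximum.

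**Event definition.** SAP 3.8.1 defines PFS time to the first confirmed progression, clinical or radiological, or death. A subject without documented progression "will be censored at the date of the last tumor response assessment, date of start of alternate therapy", or last contact in post-study follow-up, whichever comes first. Protocol 4.1.1.2 and SAP 2.2.3.2 instead use the earliest progression and do not mention confirmation.

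**Imaging.** Both flowcharts in Protocol 3.2 place scans at the start of Cycles 4, 7 and 10. After treatment the scan is due "84 ± 7 days from last disease assessment". Neither lists a repeat scan at 4 weeks.

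**Leaving treatment or study.** Under Protocol 3.1.10.1, subjects with RECIST 1.1 progression "will be allowed to continue on therapy until confirmation of progression if the subject agrees" and the investigator finds certain clinical conditions met. Protocol 3.1.10 adds: "Subjects who begin other anti-cancer therapy should immediately be considered off-study".

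**The concern.** The first on-treatment scan, at Day 85, falls exactly on the 12-week limit, so the confirmation rule applies where early failures first become visible. A subject whose scan shows growth and who then stops, or changes therapy, may never have the second scan. Neither document says what her unconfirmed irPD counts as. If SAP 3.8.1 is applied as worded, she is censored at about Day 85.

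That censoring is informative, because the reason for it is a failing scan. Kaplan-Meier would treat her as having the same outlook as subjects whose Day 85 scan was clear. The irRECIST 6- and 12-month rates and median, all listed secondary endpoints, would be too high. A gap between irRECIST and RECIST 1.1 results could then be read as pseudo-progression when part of it came from missing scans.

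**Working it through.** **The plan's own figure.** The only sizing figure, 41 subjects and 80% power for 25% against 45% (Protocol 3.1.6), concerns RECIST 1.1. It reproduces: with an exact one-sided test, at least 16 of 41 successes gives alpha 0.033 and power 0.823. It is not in dispute here, and the plan gives no figure for irRECIST.

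**Step 1: dates.** Inputs are the row "Target Cumulative Visit Day" and the follow-up columns of the flowcharts.

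- Twelve weeks after Day 1: 1 + 84 = Day 85, which is Cycle 4 Day 1. The visit window is Days 82-88, so scans on Days 86-88 fall outside the early-irPD rule.
- Next scan: 85 + 84 = Day 169, window 162-176. This is more than 4 weeks later, so it can confirm.
- End of Study is last dose + 90 ± 7 days:

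| Last dose | End of Study | Against scan window 162-176 |
|---|---|---|
| Q4W, Cycle 3 Day 3 (Day 59) | Day 149 (142-156) | ends 6 to 34 days too early |
| Level 0a, Cycle 3 Day 17 (Day 73) | Day 163 (156-170) | overlaps |
| PLD given on Day 85 | Day 175 (168-182) | overlaps |

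The scan is therefore missed by Q4W subjects who stop at Day 85 before dosing, and by anyone who starts other therapy.

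**Step 2: which subjects stop.** The 8.6 exception covers only rapid deterioration. The conditions in 3.1.10.1 for continuing are stricter: they also require consent, no symptoms or signs of progression, and no significant ECOG decline. A subject who declines consent, or has symptoms without rapid deterioration, fails 3.1.10.1 yet still needs confirmation under 8.6.

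**Step 3: size, by illustration.** The documents give no rate of unconfirmed irPD, so the following are assumptions: constant hazard; all progression up to Day 85 found as irPD at that scan; no capture as clinical progression; a share *w* of those irPDs needing confirmation (1, or 4/7 if only scans on Days 82-85 of the seven window days count); and a share *u* of these never re-imaged (25% or 50%).

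With true 6-month PFS *p*, S(85) = √p. The fraction censored is f = (1 − S(85)) × w × u, and the estimate is KM(169) = [S(85) + f] × p / S(85).

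Example, p = 0.25, w = 1, u = 0.5: S(85) = 0.5, f = 0.25, KM = 0.75 × 0.5 = 0.375.

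| True rate | w | u = 25% | u = 50% |
|---|---|---|---|
| 25% | 4/7 | 28.6% | 32.1% |
| 25% | 1 | 31.2% | 37.5% |
| 45% | 4/7 | 48.2% | 51.3% |
| 45% | 1 | 50.5% | 56.0% |

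Every estimate after Day 85 carries the same multiplier, [S(85) + f] / S(85). It is 1.14 to 1.50 for a true 25% and 1.07 to 1.25 for a true 45%. The 12-month rate is inflated in the same proportion.

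**Step 4: the same effect in subjects.** Take 41 subjects, 10 truly event-free at 6 months (24.4%), with 10 to 20 irPDs on Day 85 (E) and the rest at Cycle 7 (L = 31 − E). If k of the early ones are censored, KM = [1 − (E − k)/41] × [1 − L/(41 − E)]. For k = 2 this is 26.0-26.7%; for k = 5, 28.3-30.2%. With 18 event-free (43.9%, L = 23 − E), k = 2 gives 46.7-48.1% and k = 5 gives 51.0-54.4%.

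**The case against.** The strongest reply is that the affected group may be small. It has several parts, and most of them stand.

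- A reader might infer that subjects who stop have no repeat scan scheduled. That is not so. Both flowcharts schedule one, and because 8.6 sets no maximum interval it can confirm the irPD. It is lost only in the cases in Step 1.
- Stopping at the Day 85 scan is not the default path. Section 8.6 has dosing continue, and Protocol 3.1.10 lists withdrawal from treatment for progression only once irRECIST progression is confirmed.
- A reader might also infer that the clinical-progression route in SAP 3.3.1 is closed because she has a scan. The wording concerns imaging being unavailable to determine irRECIST status, and a missing confirmatory scan arguably fits. The irRECIST endpoints there include clinical progression and death. The route is permitted, however, not required.
- Progression dates are collected every 3 months after the study (Protocol 3.1.16). That helps, but they may come from outside records with no irRECIST reading, and the SAP does not say whether they confirm an earlier irPD.
- The documents do not uniformly direct censoring. The irPD definitions in Protocol 8.6.1 and 8.6.4 and SAP 3.3.1 contain no confirmation term, and two of the PFS definitions use the earliest progression. This is correct, and it means that two programmers could code the same subject in opposite ways.

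The SAP rule that counts dropouts as progressed does not close the gap. It is stated only for the binomial sensitivity analysis of the primary hypothesis.

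**Conclusion.** The event definitions conflict, and an early irPD that is never re-imaged has no stated outcome. Under the SAP 3.8.1 wording, a subject who misses the later scan and is not captured as clinical progression or death is censored at about Day 85. The bias is upward, and it affects the irRECIST 6- and 12-month PFS rates and median.

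The size is unknown. The ranges of about 29-38% for a true 25% and 48-56% for a true 45% rest on assumed shares of 25-50% not re-imaged. They are upper-end figures for those shares, since they allow nothing for clinical capture, for rapid deterioration or for deaths before the scan. The documents do not support saying that irRECIST PFS will exceed RECIST PFS because of missing scans, only that it could.

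The stakes are limited: these are secondary endpoints with no hypothesis test, RECIST 1.1 PFS is tabulated alongside, and the primary RECIST 1.1 endpoint is not subject to the 8.6 rule.

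**What to change.** 1. Reconcile SAP 3.8.1 with SAP 2.2.3.2 and Protocol 4.1.1.2 on whether a PFS event needs confirmation.
2. Add to SAP 3.3.1 and 3.8.1, for the irRECIST analyses: *An early irPD with no later evaluable scan, because the subject stopped treatment, started other anti-cancer therapy, withdrew or died, counts as an event on the date irPD was first documented; only a later scan that no longer meets irPD criteria cancels it.*
3. Report the analysis that censors these subjects as a sensitivity analysis, with their number.

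The cost is SAP wording and one extra analysis; no scans are added. The downside is that an occasional pseudo-progression that is never re-imaged counts as an event, and the sensitivity analysis shows how much that matters.
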